Procedure. Following the in-person screening procedure and confirmation of eligibility, participants will be asked to complete 4 sessions the first of which will begin immediately following the in-person screening (or a day/time that is more convenient for the participant). Subsequent sessions must be scheduled at least 48 hours apart. Participants are not required to abstain from nicotine/tobacco (as we are not testing the ability of these products to suppress abstinence related symptoms or measure acute self-administration behavior), food, or caffeine prior to any session.

Of note, research staff will use Zoom, as an intercom to communicate with participants whenever possible during sessions.

At the start of the session, participants will be asked about symptoms experienced since their last visit (with the exception of session 1, if completed at the in-person screening session; see Presession symptom Checklist). Answers given about respiratory and gastrointestinal symptoms will be compared to the participants' previous answers, and if any symptoms have become more frequent or more severe, the medical monitor and/or study nurse will be asked to review the symptoms. In some cases, we may contact [name] to determine if a session can proceed.

Next, participants will have their breath tested (expired carbon monoxide [CO]) and physiologic data collection will begin. We will check blood pressure once at the beginning of the session and again at the end. Heart rate will be measured continuously throughout the session. Immediately after session onset, participants will have a 30-minute rest period.

During rest periods, participants will not be allowed eat or drink outside beverages, but we will provide water to drink and they are invited to use their phone, read books/magazines, or watch movies that we provide to them.

After the 1st rest period, participants will complete subjective measures 1. Immediately after completing subjective measures 1, participants will sample the session-specific product (5 self-directed ECIG/own brand cigarette puffs over 10 minutes). After sampling is complete they will complete subjective measures 2. Ten minutes after their sampling has been completed, they will complete the DPT/CP-DPT. The DPT/CP-DPT takes approximately 10 to 15 minutes to complete. Please note at session 1, only the DPT will be completed, blood pressure will be checked, physio data collection will end, and then the session will end.

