In sessions 2 and 3 and 4, after completing the 1st DPT/CP-DPT, participants will start the 2nd 30-minute rest period. After the rest period, participants will complete subjective measures 3. Immediately after subjective measures 3, participants will sample the other session-specific product (5 self-directed ECIG puffs over 10 minutes). After sampling is complete they will complete subjective measures 4. Ten minutes after their sampling has been completed, they will complete the DPT/CP-DPT.

After completing the 2nd DPT/CP-DPT, blood pressure will be checked, physio data collection will end, and participants will be paid for their time.

The study procedures for session 1 should take no more than 70 minutes or 1.2 hours, and for sessions 2 and 3 and 4 should take no more than 140 minutes or 2.3 hours.

Please note there can be some variability in the session times due to participant behavior (i.e., taking shorter/longer than expected to complete measures/tasks).

Session Timeline:

0m – eCO Check; Physiologic data collection begins, additional questions asked.
5m – Begin 30m Rest Period 1
35m – Subjectives 1
40m – Sample Product 1 (puffs)
50m – Subjective 2
60m – 1st DPT/CP-DPT
75m – Begin 30m Rest Period 2 / Physiologic data collection ends; Session 1 end
105m – Subjectives 3
110m – Sample Product 2 (puffs)
120m – Subjective 4
130m – 2nd DPT/CP-DPT
140m – Physiologic data collection ends; Session 2/3/4 end

Note: Product sampling will consist of 5 self-directed sample puffs for own brand cigarettes or ECIG conditions taken over 10 minutes.

Measures.

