Baseline measures. During the in-person eligibility screening, we will assess sociodemographic and income-related information, discounting, health and psychiatric conditions, drug and alcohol use, history and patterns of tobacco use, nicotine dependence/craving, and perceived harm and risk of tobacco products using standardized items from national surveys (e.g., Behavioral Risk Factor Surveillance Survey; Tobacco Use Supplement to the Current Population Survey). Urine samples will be tested immediately for cotinine (a major nicotine metabolite) using the NicAlert semi-quantitative test (Jant Pharmaceutical Corporation, Encino, CA), and among women for pregnancy. For eligible/enrolled participants, we will retain a urine sample (≤ 10 ml) for later analysis of tobacco-related biomarkers. We will also be obtaining baseline physiological measures including: eCO and HR/BP. eCO will be assessed via a BreathCO monitor (Vitalograph, Lenaxa, KS). HR/BP will be measured and saved electronically using software and equipment that sounds an alarm if safety parameters are exceeded (Model 506, Criticare Systems).

The Minute Discounting Task is a series of hypothetical decision scenarios. Each scenario presents a choice between receiving an amount of money now or an amount of money later. These choices are differentiated by the amount of money at each time point and the length of time between the time points. Participants make a choice for five decision scenarios which are automatically adjusted based upon individual responses; while there are approximately 30 potential scenarios, only five are presented to the participant. The task takes less than one minute to complete. Data is collected via Qualtrics survey. Data is stored within Qualtrics under usernames and passwords assigned to some lab staff.

Physiological measures. Physiological measures are being collected primarily for participant safety during sessions. For eligible/enrolled participants, up to 10 ml of urine collected at the in-person screening session will be saved and frozen for later analysis of tobacco-related biomarkers including nicotine and its metabolites (i.e., cotinine), propylene glycol, and (4-(methylnitrosamino)-1-(3-pyridyl)-1-butanol) (NNAL). HR/BP will be measured and saved electronically using software and equipment that sounds an alarm if safety parameters are exceeded (Model 506, Criticare Systems).

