2. * Describe any potential harms or discomforts that participants could experience during the intervention activity:

Physical Risks:

1. You may experience mild frustration while completing some of the study-related tasks.
2. On very rare occasions, you may experience small droplets of liquid during inhalation of the e-cigarette we provide. You may find these droplets to be unexpected and/or unpleasant. This experience has been reported by e-cigarette users, and they report that it is an annoyance that does not appear to present any known medical danger. If this occurs, we will immediately replace the e-cigarette device you are using.
3. The e-cigarette liquid that we give you may contain less or more nicotine than you are used to, although some e-cigarette users report using these products. Inform the study staff immediately if you experience any discomfort. You may also experience side effects from products that contain nicotine such as acute increases in heart rate and blood pressure, sweating, lightheadedness, dizziness, nausea, and nervousness. These side effects are unlikely in individuals who use cigarettes regularly.
4. The Centers for Disease Control and Prevention advises that e-cigarette, or vaping products are unsafe for youths, young adults, or women who are pregnant. Adults who do not currently use tobacco products should not start using e-cigarette, or vaping, products. If you use e-cigarette products, monitor yourself for the below symptoms and promptly seek medical attention if you have concerns about your health.
 - a. Some people who use e-cigarettes have reported experiencing seizures. Some of these individuals reported a prior history of seizures or using other substances at the same time as their e-cigarette.
 - b. In some cases, e-cigarette use has led to respiratory illnesses such as difficulties breathing, shortness of breath, cough, and/or chest pain before hospitalization. In some cases, e-cigarette use has led to death, although most of these cases have been related to vaping THC.
 - c. In some cases, e-cigarette use has been associated with symptoms of mild to moderate gastrointestinal illness such as nausea, abdominal pain, vomiting, diarrhea, fevers, or fatigue.
5. The use of e-cigarettes may include other side effects/risks such as a sore or scratchy throat and headache.

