In addition, non-invasive computerized monitoring equipment allows for minute-by-minute, real-time monitoring of participants' heart rate. If needed, we can monitor blood pressure as well throughout the session. Research personnel are trained to alert the research nurse if heart rate continually exceeds 120 beats per minutes, if systolic BP continually exceeds 160 mm Hg, or if diastolic BP continually exceeds 100 mm Hg. Individuals whose heart rate and/or BP levels remain elevated will be monitored by the nurse, and if necessary emergency responders will be notified. Emergency medical coverage is available via the emergency room that is approximately 1.5 miles from the CSTP.

We screen for pregnancy among participants to reduce these risks and inform participants of risks to the baby, during pregnancy/delivery, as well as negative fertility-related effects. We advise participants not to become pregnant or father a baby during the study.

We also inform participants of unknown negative effects related to study participation. Being open about these risks is an important step.

We also monitor the research literature and public health authorities for any changes in risks associated with cigarette smoking and/or ECIG use.

3. * Describe any potential risks or harms to a community or a specific population based on study findings (e.g. information that could be stigmatizing or derogatory):

None

4. Where appropriate, discuss provisions for ensuring necessary medical, professional, or psychological intervention in the event of adverse events to the subjects:

Research personnel are trained to alert the research nurse if heart rate continually exceeds 120 beats per minute, if systolic BP continually exceeds 160 mm Hg, or if diastolic BP continually exceeds 100 mm Hg. Individuals whose heart rate and/or BP levels remain elevated will be monitored by the research nurse and if, necessary, emergency responders will be notified. Emergency medical coverage will be available via the emergency room that is 1.5 miles from the CSTP.

Individuals whose BP levels are elevated (≥ 140 mmHg systolic or ≥ 90 mmHg diastolic) during baseline screening or at a session will be provided with a blood pressure information sheet by the research staff (see study document). This sheet will be provided at the first instance of elevated blood pressure observed during the study.

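### In sessions 2–4 no blood pressure reading is scheduled between the two products, so a rise after the first would not show on any scheduled reading before the second

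*Combined protocol and SAP*

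**What the plan says.** All places are in the combined protocol and SAP.

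- **Study Procedures, item 7, Procedure:** "We will check blood pressure once at the beginning of the session and again at the end". Heart rate is recorded continuously. For sessions 2–4 the end reading is placed as follows: "After completing the 2nd DPT/CP-DPT, blood pressure will be checked, physio data collection will end, and participants will be paid for their time". In session 1, which has one product, blood pressure is checked after the first purchase task, when the session ends.
- **Session Timeline:** product 1 at 40 minutes, product 2 at 110, end of sessions 2–4 at 140. The 75-minute line is both the start of Rest Period 2 and the end of session 1.
- **Risks, Discomforts, Potential Harms and Monitoring, item 2:** staff are trained to "alert the research nurse if heart rate continually exceeds 120 beats per minutes", and likewise "if systolic BP continually exceeds 160 mm Hg, or if diastolic BP continually exceeds 100 mm Hg". Just before this the plan says "If needed, we can monitor blood pressure as well throughout the session". The same item provides for an available nurse and for possible withdrawal after repeated high blood pressure. Item 5 allows withdrawal for safety concerns.
- **Measures:** heart rate and blood pressure are taken with "equipment that sounds an alarm if safety parameters are exceeded". Physiological data are collected mainly for safety.
- **Behavioral Intervention/Task Details, item 2:** "Inform the study staff immediately if you experience any discomfort".
- **Pertinent Results and Incidental Findings, item 5:** when blood pressure is high, staff seek guidance from the medically responsible investigator and/or the PI.
- **Symptoms at session start (Procedure):** "if any symptoms have become more frequent or more severe, the medical monitor and/or study nurse will be asked to review the symptoms".

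**The concern.** The plan names an acute rise in blood pressure as a possible nicotine effect and collects physiological data chiefly for safety. Yet in the three sessions that give two nicotine products, both scheduled readings fall outside the interval between them. The first predates any product and the second comes when nothing is left to withhold. A rise caused by product 1 could reach staff before product 2 only through another channel: heart rate, the participant's own report, or a reading that someone chooses to take.

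The alert rule adds to this. It is triggered when pressure continually exceeds a limit, which one value cannot show, and only one value is scheduled before product 2.

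What is at stake is a small safety margin. Exposure is five puffs per product in current smokers who must have blood pressure below 160/100 at screening (Study Population, item 5). The study was submitted as not greater than minimal risk (Review Setup, item 4).

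**Working it through.** **Step 1. Reproduce the timeline for sessions 2–4 from the stated durations.**

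- Start 5 + rest 30 + subjective measures 5 = 40: product 1
- 40 + 10 sampling = 50; 50 + 10 wait = 60: first purchase tasks
- 60 + 15 for the tasks = 75: Rest Period 2
- 75 + 30 rest + 5 subjective measures = 110: product 2
- 110 + 10 sampling + 10 wait = 130: second tasks; 130 + 10 = 140: end

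This matches the printed timeline.

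**Step 2. Age of the last scheduled blood pressure at product 2** = start of product 2 − time of the first reading. The minute of the first reading is not stated; 0 to 5 minutes is assumed, before Rest Period 1. The tasks are said to take 10 to 15 minutes, so both ends are shown.

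| First tasks take | Product 2 starts | Reading at 0 | Reading at 5 |
|---|---|---|---|
| 15 min (as printed) | 110 | 110 min old | 105 min old |
| 10 min | 105 | 105 min old | 100 min old |

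The range is 100–110 minutes. The reading precedes product 1 by 40 − 5 = 35 to 40 − 0 = 40 minutes in every case. Nothing in the narrative or the timeline schedules another reading before product 2.

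**Step 3. The same quantities with a reading at the start of Rest Period 2.**

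- Time since product 1 sampling ended: 75 − 50 = 25 min (70 − 50 = 20 if the tasks take 10)
- Age at product 2: 110 − 75 = 35 min (105 − 70 = 35)
- Scheduled readings before product 2: from 1 to 2

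**Step 4. Does this let the alert rule operate?** Take a normal start value and a high value at 75 minutes. That is one high reading, so continually exceeding the limit is still not shown. A repeat that is also high gives two in a row. The repeat, not the 75-minute reading alone, is what lets the rule operate before product 2.

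**Step 5. Cost.**

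- Now: 4 sessions × 2 = 8 readings per completer; 8 × 36 = 288
- With the change: 8 + 3 = 11; 11 × 36 = 396; difference 396 − 288 = 108
- Repeats: only the 3 × 36 = 108 new readings can trigger one. If 0–10% exceed the limit (assumption), that is 0 to 10.8 repeats, for 108 to 118.8 extra readings, or 3.0 to 3.3 per completer
- Time at 1–2 min each (assumption): 3.0 × 1 = 3.0 to 3.3 × 2 = 6.6 min per completer
- Session time: 70 + 3 × 140 = 490 min; 3.0/490 = 0.6% and 6.6/490 = 1.3%

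These figures describe the schedule and its cost. They do not estimate events missed.

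**The case against.** The strongest reply is that this is a coherent choice, openly stated. The plan treats both products as one small exposure (5–10 puffs in all per session), no more than ordinary use. It brackets that exposure with two blood pressure readings and runs heart rate throughout. Participants need not abstain from nicotine before sessions. No passage promises a reading before each product. The sentence allowing extra readings directly precedes the alert rule and can be read with it, so that continually presupposes repeat measurement. Staff training content and the uploaded monitor manual are not available to us, so an instruction to recheck may exist.

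Most of this stands, and it rules out three stronger readings that a reader might infer:

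- *That participants are unmonitored between products.* They are not: heart rate is continuous with a nurse alert above 120 beats per minute, and extra readings and self-report are available.
- *That a high start reading has no consequence.* It can lead to guidance from the medically responsible investigator or PI, or to withdrawal. The order relative to sampling is not spelled out, but the route exists.
- *That the plan breaks its own alert rule.* It does not: the rule can be met whenever staff add a reading.

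What the reply does not remove is that none of these safeguards schedules a blood pressure value after product 1 and before product 2. The option of extra readings comes with no trigger or time. On blood pressure, the equipment alarm can respond only to readings actually taken.

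**Conclusion.** The point holds in a narrow form and is minor. In sessions 2–4 the last scheduled blood pressure before the second product is about 100–110 minutes old and predates the first, so a rise after product 1 cannot appear on a scheduled reading in time. Other safeguards reduce the risk but do not supply that value.

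This rests on the printed timeline, the assumed 0–5 minute window for the first reading, and task times of 10–15 minutes. The documents give no rate of high readings during sessions and no time course of blood pressure after five puffs. Neither the number of rises that would be caught nor the share still visible 25 minutes after sampling can be estimated. No aim, outcome or analysis is affected. The case for change is that the step is cheap and session 1 already takes a reading at the same point.

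**What to change.** In Study Procedures, item 7 (Procedure and Session Timeline), add for sessions 2–4 one cuff reading at 75 minutes, the start of Rest Period 2. If it is above 160 systolic or 100 diastolic, repeat it during that rest period. If the repeat is also above, alert the research nurse and hold the second product pending review by the PI or medical monitor. These are the limits of the existing alert rule. Leave the heart-rate alert and the option of extra readings as they are.

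The cost is protocol wording, 108 extra automated readings over 36 completers and, under the assumptions above, up to about 11 repeats, or roughly 3 to 7 minutes per completer. Expect a few more nurse alerts and an occasional held or rebooked session, which the minutes do not include. The reading follows the first purchase tasks, so Subjectives 2 and those tasks are undisturbed, and a repeat fits within the 30-minute rest.

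A similar hold rule for start readings in all sessions, or a written definition of continually, would be optional wording. Neither is needed for this change.

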1. May participate in any study interaction or intervention (Including screening, consenting, and study activities)

AND/OR

2. You obtain any data/specimens about (regardless of identifiability)

at VCU and at other sites under the VCU IRB's oversight. See the help text for additional guidance.

100

2. If this is a multi-Center Project, what is the maximum anticipated number of subjects across all sites?

N/A

3. * Provide justification for the sample size by explaining how you arrived at the expected number of participants and why this number is adequate for answering the research questions:

This study manipulates e-cigarette flavor and nicotine flux systematically, testing the hypothesis that abuse liability will be related directly to flux or flavor among a sample of cigarette smokers. Previous studies using this type of design are limited.

Thus, we calculated a sample size to achieve a power of >0.80 with $\alpha < 0.05$ and assuming a small effect size (Cohen's $f=0.20$) and moderate repeated measures correlation ($r=0.5$) in a repeated measures ANOVA with nicotine flux as within-subjects factors ($N=32$; GPower).

In this study, 36 cigarette users will attend the lab for 4 sessions: 1) own brand cigarette (always the first session), 2) NJOY Ace 2.4% nicotine ECIG (Menthol and Classic Tobacco flavor), 3) NJOY Ace 5.0% nicotine ECIG (Menthol and Classic Tobacco flavor), and 4) NJOY Daily ECIG 6% nicotine (Menthol and Extra Rich Tobacco).

We hypothesize that flux will be positively associated with willingness to pay (drug purchase task) and willingness to substitute e-cigarettes for own brand cigarettes (cross-product drug purchase task), and inversely to price sensitivity (drug purchase task) for all smokers.

We hypothesize that within class, menthol flavored products will be positively associated with willingness to pay (drug purchase task) and willingness to substitute e-cigarettes for own brand cigarettes (cross-product drug purchase task), and inversely to price sensitivity (drug purchase task) for all smokers.

It is possible that we would consent up to 100 participants in order to obtain 36 participants who complete the entire study.

4. * List the study inclusion criteria:

All participants must be healthy (determined by self-report), at least 18 years old (verified by photo ID), willing to provide informed consent, and attend the lab. Participants must agree to use designated products according to the study protocol.

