Behavioral measures. Our primary behavioral measures are two behavioral choice tasks (Drug Purchase Task; Cross Product-Drug Purchase Task).

The Drug Purchase Task (DPT) assesses hypothetical tobacco product purchasing behaviors for a tobacco product. Please note this measure is tailored to own brand cigarette puffs and ECIG puffs. The outcomes from the DPT include the breakpoint (highest price participants were willing to pay), elasticity (change in amount purchased as price increases), Omax (highest amount individuals paid in any choice, i.e., maximum value of price*quantity), Pmax (the price associated with Omax), and intensity (amount “purchased” when the price is zero/free). Data is collected via REDCap survey and stored under username/password with specific access per user.

The Cross Product (CP)-DPT assesses cross-product purchasing behaviors between various tobacco products offered at a fixed amount and own brand cigarettes offered at varying prices (\$0-20.48). Please note this measure is tailored to ECIG puffs. The main outcome for the CP-DPT is cross-price elasticity, or the extent to which purchasing of the session-specific product increases when the price of own brand cigarettes increase. Both the DPT and CP-DPT tasks are programmed to end early if participants report zero consumption for assessed products. Estimated time per measure is <3 min. Data is collected via REDCap survey and stored under username/password with specific access per user.

Subjective measures. Repeatedly within each condition we will use the Adapted Hughes/Hatsukami Questionnaire, the Direct Effects of Nicotine Scale, the Direct Effects of Tobacco Scale, Pennington VAS Scale and several items that utilize the Generalized Labeled Magnitude Scale and the General Labeled Hedonic Scale to measure tobacco abstinence symptoms and other effects before and after each product sampling.

Subjectives 1 and 3 will not include product-specific questions (Direct Effects of Tobacco Scale, Generalized Labeled Magnitude Scale and the General Labeled Hedonic Scale).
Subjectives 2 and 4, will include product-specific questions.

We will also ask a validation question during Subjectives 2 and 4 related to flavor of the product that was tried.

All data is collected via REDCap or Qualtrics survey and stored under username/password with specific access per user.

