Tobacco Cessation Resources. A brief handout containing information about tobacco cessation and available resources will be provided to all participants who consent to this study. Participants are not required to take the handout. This handout will be given at the end of their study participation (at screening if ineligible, at the end of their last study session, or via email if they self-withdraw or are withdrawn by the PI/medical monitor). We provide this information as it may assist individuals who are considering quitting tobacco now and/or quitting tobacco in the future.

Data analysis. Subjective, physiological, and behavioral data will be prepared as reported elsewhere (e.g., [name] et al., 2017; Rusted et al., 1998; [name] et al., 2010). Elasticity is estimated using an exponential demand function with nonsystematic DTP data excluded based on two criteria: trend, or whether the participant had a general decrease in consumption from the lowest to highest price; and bounce, or whether a participant reported higher consumption at sequential higher prices (Stein et al., 2015). In general, analysis will involve a mixed (between- and within-subject) ANOVA. Demographic data will be examined to determine if there are significant between-group differences on measures that may be related to study outcomes. Unexpected between group differences will be considered as potential covariates in the primary analysis (see Evans et al., 2006). Statistical analyses may utilize regression, ANOVA, or mixed linear models. Adjustments for sphericity violations and post-hoc testing using Tukey's HSD or planned contrasts with Bonferroni corrections will be used (Keppel, 1991). Based upon the type and amount of missing data, we may use accepted techniques such as multiple imputation (Allison, 2001).

8. * The IRB only reviews research activities, so indicate for each of the study activities described in the question above or in the protocol which activities are:

- Being performed exclusively for research purposes (i.e. they would not otherwise be done apart from this study) **VERSUS**.
 - Alterations of routine activities/procedures (e.g. the study is altering the timing, frequency, method, location, amount, etc.) **VERSUS**.
 - Being done for other purposes and whose data/results will be used secondarily in the study (e.g. standard medical or psychological tests, routine education practices, quality improvement initiatives, etc.).
- See the help text for additional guidance

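### For the subjective scales taken before and after each sampling, the plan does not prespecify adjustment for the pre-sampling score, a near-free gain on some secondary outcomes

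*Combined protocol and SAP*

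**What the plan says.** Study Procedures, item 7, Procedure and Session Timeline: Subjectives 1 is completed immediately before the first product is sampled and Subjectives 2 after it. In sessions 2 to 4 a 30-minute rest follows the first purchase tasks. "After the rest period, participants will complete subjective measures 3", the second product is then sampled, and Subjectives 4 comes after it.

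The Subjective measures paragraph says the scales serve "to measure tobacco abstinence symptoms and other effects before and after each product sampling". It leaves three product-specific sets out of Subjectives 1 and 3: the Direct Effects of Tobacco Scale, the Generalized Labeled Magnitude Scale and the General Labeled Hedonic Scale. The Adapted Hughes/Hatsukami Questionnaire, the Direct Effects of Nicotine Scale and the Pennington VAS therefore have a score on both sides of each sampling. The primary behavioral measures (DPT and CP-DPT) are given only after sampling.

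On analysis, the Data analysis paragraph says "In general, analysis will involve a mixed (between- and within-subject) ANOVA". On covariates it says "Unexpected between group differences will be considered as potential covariates in the primary analysis", in the context of demographic data. It also allows regression or mixed linear models and refers to outside sources for data preparation. It mentions neither the pre-sampling score, nor a change score, nor a pre/post time factor.

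**The concern.** Starting state is not standardized. The Procedure paragraph requires no abstinence from nicotine, food or caffeine before a session, so a participant's symptom level before sampling can differ from session to session. The trial already records that level. If it predicts the post-sampling score within a person, leaving it out puts the variation into the error term of every product and flavor contrast on these scales.

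The one covariate strategy that is named does not address this. A demographic characteristic is constant within a participant, so in balanced data its main effect cancels from every within-person contrast. The plan thus names a covariate rule that cannot sharpen the product comparisons and is silent on one that can. The silence also leaves post-only, change-score, time-factor and covariate-adjusted analyses all open, so the choice could be made after the data are seen.

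**Working it through.** **Inputs.** From Study Population, item 3: f = 0.20, alpha 0.05, between-condition correlation r = 0.5, stated N = 32, and 36 completers planned ("It is possible that we would consent up to 100 participants in order to obtain 36 participants who complete the entire study"). From the aims: four conditions for Aim 1 (own brand plus three tobacco-flavor e-cigarettes) and two flavors within each e-cigarette class for Aim 2. Assumed, because the documents give no value: the within-person, session-level pre-post correlation ρ, shown at 0, 0.3 and 0.5. It is not the r = 0.5 of the sample-size paragraph, which is a correlation between conditions.

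**Formula.** For a one-group within-subject factor with m levels under sphericity:
λ = f²·N·m/(1 − r)/V, df₁ = m − 1, df₂ = (N − 1)(m − 1).
V is the within-person error variance relative to a post-only analysis. Adjustment for a session-level pre-score gives V = 1 − ρ², so V = 0.75 at ρ = 0.5 and 0.91 at ρ = 0.3. The covariate costs one error degree of freedom, which changes the powers below by no more than 0.001.

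**The plan's own figure.** With m = 4 and N = 32, λ = 0.04·32·4/0.5 = 10.24 and power is 75.3%, so N = 32 does not reproduce for four levels. Reaching 80% takes 36 at m = 4 and 42 at m = 3. N = 32 does come out at m = 5 (81.4%). The number of measurements is not stated, so the figure is not shown to be wrong, and the planned 36 completers give 80.8% at m = 4.

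**Effect of adjustment at N = 36.**

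| Contrast | λ, post-only | Power, post-only | λ at ρ = 0.5 | Power at ρ = 0.5 | Power at ρ = 0.3 |
|---|---|---|---|---|---|
| Two flavors (m = 2) | 5.76 | 0.646 | 7.68 | 0.769 | 0.687 |
| Three e-cigarette levels (m = 3) | 8.64 | 0.733 | 11.52 | 0.854 | 0.775 |
| Four conditions (m = 4) | 11.52 | 0.808 | 15.36 | 0.913 | 0.847 |

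At ρ = 0.5 the gain is 10.5 to 12.3 points; at ρ = 0.3 it is about 4. At ρ = 0, V = 1 and there is no gain over post-only.

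**Simulation** (m = 4, N = 36, 6,000 runs). At ρ = 0.5: post-only 79.8%, change score 80.7%, adjusted 91.0%. At ρ = 0: post-only 80.7%, change score 49.0%, adjusted 80.2%.

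**Why ρ must be within-person.** With r = 0.5, half the variance is stable between people, and the within-subject analysis already removes it. An overall pre-post correlation of 0.5 could be all between-person (0.5·1 + 0.5·0), which gives ρ = 0 and no gain. It could also be evenly split (0.5·0.5 + 0.5·0.5), which gives ρ = 0.5 and the gain in the table.

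**Own brand.** Suppose the own-brand pre-score is shifted by one within-person SD and the shift has gone by the post-sampling score. At ρ = 0.5, adjustment moves the own-brand contrast by −0.5 × 1 = −0.5 SD, while the post-only contrast is unbiased. The variance factor for a pairwise contrast is then about 0.75·[1 + (1/105)/(2/36)] = 0.88, where 105 = 35·3 is the residual degrees of freedom for the pre-score. Simulation gives about 0.89. If the shift persists after sampling, post-only is the biased analysis.

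**The case against.** The strongest reply is that silence is not a decision. The Data analysis paragraph permits mixed linear models, which is the form of the remedy, and it defers data preparation to sources that may define how pre-scores are used. A reader might infer that the plan rejects the pre-score or commits to post-only scores. The text does not support that; it supports only that the adjustment is not prespecified.

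A reader might also infer a fixed loss of 10 to 12 points, or a loss of power for the trial's main question. Neither follows. The gain runs from nothing upward according to a correlation that the documents do not give. The f and r are borrowed from a calculation whose hypotheses concern the purchase tasks, and those have no pre-sampling score. The steep loss under a change-score analysis at ρ = 0 (power 0.43 for three levels, with V = 2) is likewise the cost of an analysis that the plan never specifies.

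Subjectives 3 follows the first product in the same session, so one might conclude that residual effect biases the second product's result. The Overview builds flavor order into the Latin square and the Procedure puts a 30-minute rest before Subjectives 3, so equal carryover balances across flavors. What remains is added error, not a demonstrated bias.

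Own brand is different. It is always first, is outside the Latin square, and may directly follow screening, so its starting state can differ systematically from the later sessions. Adjusted and unadjusted analyses can then answer different questions, and a rule that adjustment must replace the post-only analysis everywhere would not be justified. That part of the objection stands.

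Demographic covariates also keep a role in between-group comparisons and in product-by-covariate interactions. The point here is confined to their main effects in within-person contrasts.

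**Conclusion.** The point holds as a low-severity efficiency and prespecification gap. It concerns only the subjective scales given both before and after sampling, and adjustment is clearly preferable only for contrasts among the e-cigarette conditions assigned by Latin square. For those, at N = 36, f = 0.20 and r = 0.5, the gain is about 12 points (0.73 to 0.85 for three levels, 0.65 to 0.77 for two flavors) if the within-person pre-post correlation is 0.5, about 4 points at 0.3, and essentially none at 0. The four-condition gain (0.81 to 0.91) further assumes that starting state does not differ systematically at the own-brand session. DPT, CP-DPT and the three product-specific scale sets are unaffected.

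**What to change.** In the Data analysis paragraph, for each scale given at Subjectives 1/3 and 2/4, prespecify a mixed linear model of the post-sampling score over the Latin-square e-cigarette conditions. Include product and flavor, order, participant, and that sampling's own pre-sampling score split into the participant's mean and the deviation from it. State that demographic between-group tests will not select covariates for these product contrasts.

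For contrasts with own brand, report the adjusted result alongside the unadjusted post-score result as a sensitivity analysis, and explain that the two can differ if starting state differs at the first session.

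The cost is a few sentences, one or two model terms and about one error degree of freedom. No new data, visits or participants are needed.
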